## 7.0 STUDY PROCEDURES

## 7.1 Pre-Screening Visit by Screening Dentist

Pre-Screening Visits can be conducted by a Screening Dentist (SD). Screening Dentists are general dental practitioners that normally refer patients for endodontic treatment to an endodontist. For the purpose of the study, Screening Dentists are the dentists who are part of

the study and are trained on the screening aspect of the study. Patients that appear to be eligible will be initially contacted through the Screening Dentist's own patient pool.

A patient will visit the Screening Dentist, according to standard of care, to be evaluated for root canal therapy.

The Screening Dentist will, according to standard of care, use a Screening Protocol and Screening Form (*see Appendix III. Screening Protocol*) to evaluate:

- 1. The patient's medical and dental health
- 2. The patient's eligibility as a study candidate

In addition, the GP or the SD should have completed the following:

- 1. Caries removal on the subject tooth and restoration, if applicable.
- 2. If caries are present underneath a crown, inlay or onlay then removal of the crown, inlay or onlay should occur in addition to caries removal and resin based restorative material restoration.
- 3. Caries removal on any tooth on the same side of the oral cavity as the subject tooth.
- 4. Extraction of partially erupted, malposed, carious, impacted wisdom tooth; and/or extraction of retained roots that may affect the outcome of root canal therapy on the subject tooth.
- 5. Treatment of any tooth on the same side of the oral cavity that has a source of pain.
- 6. Dental cleaning (full mouth) if not completed within six (6) months of Pre-Screening. In the case of patients who have heavy calculus and plaque accumulation tendencies, a full mouth dental cleaning should be completed even if the last dental cleaning was performed within six (6) months of Pre-Screening.

These above mentioned items should have been completed, as necessary, prior to screening the patient for the study according to standard of care dental procedures.

These screening candidates will be responsible for any standard of care costs associated with any of the above treatments or visits.

No Protected Health Information (PHI) will be collected on the Screening Form. The patient will be identified by a screening code on the Screening Form (*see Section 7.1.1 Screening Code*).

If the patient is successfully pre-screened, the SD will send the following to the Sponsor:

- One (1) Periapical (PA) digital and/or hard copy redacted radiograph taken within two (2) months of Pre-Screening.
- One (1) Bitewing (BW) digital and/or hard copy redacted radiograph taken within two (2) months of Pre-Screening.
- PA radiograph has to show the periradicular tissue surrounding the subject tooth roots.

- BW radiograph has to show interproximal aspects of the coronal portion of the subject tooth, teeth adjacent to the subject tooth, and the opposing teeth in that quadrant.
- Redacted camera images of the patient's smile using retractors and the occlusal surface of the subject tooth are requested. If camera images are not available, then full mouth radiographs are requested for screening.
- Completed and signed Screening Form.

In addition, the SD should send the following to the PI's clinical site designee:

- The last dental visit notes for the patient. At a minimum, this should include information on the patient's dental treatment on the subject tooth and any assessments performed at the screening visit.
- Contact information for the patient. At a minimum, this includes phone number, address, and email, if applicable.
- Any other pertinent information required for treatment.

For a particular patient the SD may submit all eligible teeth for review. This Pre-Screening submission will include separate Screening Forms, as well as pertinent radiographs and camera images for all eligible subject teeth.

The Sponsor will not accept incomplete or inaccurate submissions and will not process study payments until required items are received and verified.

Both Screening Dentists and PIs conduct a medical and dental review and assessments on a patient. The Screening Dentist performs this review only as part the pre-screening process. Information collected by a Screening Dentist will not be included as study data (i.e. Screening Form, pre-screening radiographs, and dental notes). Only information collected by a PI will be used as study data. The data collected or assessments performed by a PI supersede those completed by a Screening Dentist. Source data verification will occur using the subject's dental file.

## 7.1.1 Screening Code

The patient will be identified by a screening code. The Sponsor will generate a Screening Code for each subject tooth that is sent in for a patient on the Screening Form. (If more than one subject tooth is submitted for the same patient, each tooth will receive a unique screening code.) The screening code should be six (6) alphanumeric characters: FML-XXX. The first set of three (3) characters (FML) is the initials of the PI or Screening Dentist. If there is no middle initial, a dash will be used. The second set of three (3) characters (XXX) is a sequential number starting at 001; each screening site will start at 001. Therefore, the first patient screened by a PI or Screening Dentist with the initials ABC will have the screening code ABC-001.

### 7.2 Pre-Screening Review and Notification

#### 7.2.1 Pre-Screening by the PI

For patients pre-screened and approved by a PI, the PI will send the Screening Information to the Sponsor along with any required radiographs and camera images. The PI or a clinical site designee will schedule the patient for a Baseline Visit if the Screening Visit and Baseline Visit are not on the same day.

## 7.2.2 Pre-Screening by the Screening Dentist

For patients pre-screened by a Screening Dentist, the Sponsor will review the information provided to ensure completeness and eligibility, and, if eligible, will then forward the completed documentation to a PI for review.

#### 7.2.3 Notification of Pre-Screening Outcome to the Screening Dentist

After the PI and the Sponsor determine patient eligibility for the study, the Screening Dentist will be notified. If the patient is eligible, the PI or clinical site designee will schedule the patient for a Baseline Visit at the clinical site; at this visit; the patient will complete the screening process for the study.

#### 7.2.4 Pre-Screen Failures

If, during the Pre-Screening Process, the PI and/or the Sponsor determine that the patient is not eligible for the study, the patient will be considered a Pre-Screen Failure. Pre-Screen Failures will be treated and followed according to standard of care by their Screening Dentist or Endodontist, but will not be documented or followed for study purposes.

#### 7.3 Prior to Baseline Visit

Patients who have a tooth approved for inclusion in the study and have had sinusitis or symptoms of sinusitis within the last 3 months may be required to receive a CBCT scan prior to the Baseline Visit. If the patient is included into the study, this CBCT may be used for the Baseline CBCT scan.

#### 7.4 Baseline Visit

## 7.4.1 Informed Consent

Once the patient arrives for the Baseline Visit, the informed consent process may begin. The PI or clinical site designee will review the Informed Consent Form (ICF) with the patient *(see Appendix II. Informed Consent)*. The patient will be given the opportunity to ask questions and will be allowed sufficient time to consider the information provided. The PI will confirm the patient's understanding and consent for the study. Written consent will be obtained, which will occur prior to any data collection for the study.

In addition, the patient is informed within the ICF of possible attendance by the Sponsor and/or Sponsor representative during the Procedure Visit.

The ICF will be signed and dated by the PI, patient and clinical site designee executing the consent process. The patient shall be given a copy of the signed ICF.

## 7.4.1.1 Consent for Audio-Video Recordings and Photographs Release

In addition to the ICF, all patients will be provided with an Audio-Video Recording and Photograph Release Form. If the patient agrees and signs the ICF, the Sponsor will be able to obtain audio-video recordings and/or photographs of the patient's oral cavity and root canal treatment performed during the patient's participation in the study. The patient's participation in the study is not contingent upon agreeing to this consent.

## 7.4.2 Cone Beam Computed Tomography (CBCT) Consent

All patients will be provided with information regarding dental CBCT scanning for the study. If the patient agrees, they may be included in a study subset where dental CBCT scans will be obtained for the study.

#### 7.4.3 Screening

After the ICF has been signed, additional screening may occur to determine if the patient meets the inclusion and none of the exclusion criteria. The patient will undergo standard of care endodontic and dental assessments necessary to determine the patient's eligibility according to the Pre-Procedure Inclusion and Exclusion Criteria.

#### 7.4.4 Baseline Exam

The PI will perform the following standard of care assessments and evaluations prior to the procedure, if they were not already completed:

- 1. Medical and Dental History and Exam
  - a. Medical History: Only those histories related to endocrine/metabolic, hematologic, musculoskeletal, and immunological will be collected for the study.
- 2. Medication Regime: Only prescribed herbal or over the counter systemic antibiotics, analgesics, and anti-inflammatory medications taken during the duration of the study (24 months post procedure) and the prior three months will be documented for this study.
  - Any antibiotics, analgesics or anti-inflammatory medications provided intraprocedure by the PI during the Baseline and Procedure Visits will be collected for the study and will be documented on the Concomitant Medication Log.
  - Any antibiotics, analgesics and anti-inflammatory medications should be collected if prescribed or provided post Procedure Visit, and at all Follow-ups.
- 3. McGill Short Form Pain Questionnaire: The McGill Pain Questionnaire (MPQ) is one of the most widely used tests for the measurement of pain. It provides information on sensory, affective, and evaluative dimensions of pain experience and is capable of discriminating among different pain problems.

- 4. Gracely Descriptor Differential Scale (DDS): This scale is an intensity and unpleasantness scale. The scale includes both verbal and numeric characteristics.
- Diagnostic Radiographic Analysis: Periapical (PA) Parallel Radiograph, showing the periapical region surrounding the subject tooth should be collected for each visit. Additional radiographs completed as necessary by the PI will be collected for the study.
- 6. Periapical Index (PAI) Score analyzed by independent reviewer Up to three (3) independent reviewers will be provided radiographs in order to complete the PAI scoring. Independent reviewers will be blinded to the site, subject, and visit when completing the PAI score. This is being done to eliminate bias.
  - Score of 1: Normal
  - Score of 2: Small changes in bone structure
  - Score of 3: Changes in bone structure with some mineral loss (bone loss)
  - Score of 4: Periodontitis with well-defined radiolucent area (apical periodontitis)
  - Score of 5: Severe Periodontitis with exacerbating features (apical periodontitis)

Note: A Protocol Deviation CRF will not be completed if PAI score was not completed by an independent reviewer for a particular visit. In addition there is no defined study window for completion of PAI scoring by an independent reviewer.

- 7. Dental Cone Beam Computed Tomography (CBCT) X-rays, as applicable
- 8. Intra-Oral Examination including, but not limited to:
  - a. Tooth Number: Based on the Universal Tooth Numbering System (1-32)
  - b. Oral Hygiene: Oral hygiene should be graded on a score of Poor, Fair, or Good.
    - Poor:

There is evidence of: generalized inflammation and swelling of gingival tissue, generalized bleeding on probing and/or generalized plaque/ calculus accumulation

• Fair:

There is evidence of: localized mild to moderate inflammation of the gingival tissue, mild localized swelling of the gingival tissue, localized plaque/calculus accumulation and/or localized bleeding on probing

• Good:

There is evidence of: healthy gums and Minimal plaque. No evidence of gingival inflammation and no bleeding on probing.

c. Subject Tooth Assessments including:

- i. Probing Pocket Depth: The distance between the height of the free gingival margin and the height of attachment apparatuses below (bone, cementum, and periodontal ligament). Using a calibrated periodontal probe, the periodontal pocket depth should be recorded on the mesial, middle, and distal aspects of both the buccal and lingual sides of the tooth
- ii. Mobility
  - None: No distinguishable sign of movement.
  - Class I: The first distinguishable sign of movement greater than normal.
  - Class II: Horizontal tooth movement no greater than 1 mm.
  - Class III: Horizontal tooth movement greater than 1 mm, with or without the visualization of rotation or vertical depressability.
  - Any mobility other than none should be considered abnormal.
- iii. Swelling: This assessment includes the type and location of swelling.
- iv. Soft Tissue Lesions: This assessment includes the lesion presence, color and size where applicable. This assessment shall also include ulcerations and fistula/sinus tract.
- v. Cold Test
  - Normal: A sensation is felt, but disappears immediately upon removal of the stimulus
  - Negative: Lack of response to stimulus
  - Lingering: Lingering or intensification of a painful sensation after the stimulus is removed
  - Immediate: Excruciating, painful sensation as soon as the stimulus is placed on the tooth
  - Delayed: A painful sensation is felt after an initial delay
- vi. Root Resorption
- vii. Furcation Involvement/Furcation Defect
  - Class I: The furcation can be probed, but not to a significant depth.
  - Class II: The furcation can be entered into but cannot be probed completely through to the opposite side.
  - Class III: The furcation can be probed completely through and through.
  - Class IV: The furcation can be probed through and through, and recession reveals a visible furcation.
- 9. Endodontic Assessments including:
- a. Pulp Diagnosis:
  - Normal Pulp: A clinical diagnostic category in which the pulp is symptomfree and normally responsible to pulp testing.
  - Reversible Pulpitis: A clinical diagnosis based on subjective and objective findings indicating that the inflammation should resolve and the pulp return to normal.
  - Symptomatic Irreversible Pulpitis: A clinical diagnosis based on subjective and objective findings indicating that the vital inflamed pulp is incapable of healing. Additional descriptors: lingering thermal pain, spontaneous pain, referred pain.
  - Asymptomatic Irreversible Pulpitis: A clinical diagnosis based on subjective and objective findings indicating that the vital inflamed pulp is incapable of healing. Additional descriptors: no clinical symptoms but inflammation produced by caries, caries excavation, trauma.
  - Pulp Necrosis: A clinical diagnostic category indicating death of the dental pulp. The pulp is usually nonresponsive to pulp testing.
  - b. Periradicular Tests (Percussion and Palpation):
    - None (-): No discomfort at all.
    - Mild (+): Little discomfort, but may be noticeable by the patient.
    - Moderate (++): Some noticeable discomfort.
    - Severe (+++): Definitive discomfort.
  - c. Periradicular Diagnosis:
    - Normal Apical Tissue: Teeth with normal periradicular tissues that are not sensitive to percussion or palpation testing. The lamina dura surrounding the root is intact, and the periodontal ligament space is uniform.
    - Symptomatic Apical Periodontitis: Inflammation, usually of the apical periodontium, producing clinical symptoms including a painful response to biting and/or percussion or palpation. It might or might not be associated with an apical radiolucent area.
    - Asymptomatic Apical Periodontitis: Inflammation and destruction of apical periodontium that is of pulpal origin, appears as an apical radiolucent area, and does not produce clinical symptoms.
    - Acute Apical Abscess: An inflammatory reaction to pulpal infection and necrosis characterized by rapid onset, spontaneous pain, tenderness of the tooth to pressure, pus formation, and swelling of associated tissues.
    - Chronic Apical Abscess: An inflammatory reaction to pulpal infection and necrosis characterized by gradual onset, little or no discomfort, and the intermittent discharge of pus through an associated sinus tract.

• Condensing Osteitis: Diffuse radiopaque lesion representing a localized bony reaction to a low-grade inflammatory stimulus, usually seen at apex of tooth.

After assessments are completed, the patient may be prescribed medication(s) for pain management according to standard of care procedures. If analgesic medications need to be provided to the patient in order to complete one or more of the assessments, the assessments that require a pain response (i.e. cold test, percussion and palpation) should be completed prior to providing these medications.

Upon determining that the patient meets all the Pre-Procedure Inclusion and none of the Pre-Procedure Exclusion Criteria, the patient may proceed to the Procedure Visit.

If the patient does not meet all of the Pre-Procedure Inclusion and/or meets any of the Pre-Procedure Exclusion Criteria, the patient will be considered a Screen Failure (see Section 7.6.1 Screen Failures).

All redacted source documentation with PI signature should be provided to the Sponsor for filing after each study visit. If changes are made to the source documents after PI signature, the updated source documents should be provided to the Sponsor for filing.

Both Screening Dentists and PIs conduct a medical and dental review and assessments on a patient. The Screening Dentist performs this review only as part the pre-screening process. Information collected by a Screening Dentist will not be included as study data (i.e. Screening Form, pre-screening radiographs, and dental notes). Only information collected by a PI will be used as study data. The data collected or assessments performed by a PI supersede those completed by a Screening Dentist. Source data verification will occur using the subject's dental file.

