#### **3.3 Secondary Endpoints**

The following outcomes will be assessed:

- 1. McGill Short Form Pain Questionnaire
- 2. Gracely Descriptor Differential Scale (DDS) 59
- 3. Patient Satisfaction Survey
- 4. AAE Case Difficulty Assessment
- 5. Soft Tissue Lesions
- 6. Swelling
- 7. Root Canal Therapy Retreatment
- 8. Treatment Time
- 9. Procedure Time
- 10. Periapical Index (PAI) analyzed utilizing radiographic analysis by independent reviewer
- 11. Cone Beam Computed Tomography (CBCT) Sub-Set Evaluation
- 12. Additional Radiographic Analysis may be completed

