#### 5.2 Pre-Procedure Exclusion Criteria

- 1. Poor oral hygiene according to a Poor, Fair, Good Scale
- 2. Subject tooth with  $\geq$  Class II Mobility
- 3. Subject tooth with Periodontal Pocket Depth  $\geq 6$
- 4. Periodontal probe reaches the apex of the subject tooth
- 5. Furcation involvement originating from periodontal disease, on the subject tooth, one and/or two adjacent teeth in direct contact with the subject tooth
- 6. Subject tooth with  $\geq$  Class III endodontic furcation involvement
- 7. Subject tooth with open or incompletely formed root apices
- 8. Vertical fracture, horizontal fracture, or perforation extending below the Cemento-Enamel Junction (CEJ) of the subject tooth
- 9. Caries or another condition of the subject tooth that
  - a. prevents adequate seal of the device
  - b. requires a separate procedure for crown lengthening
  - c. requires a post

- d. provides inadequate biological width for crown retention
- 10. Any dental treatment on the subject tooth completed with the known use of devitalizers or formocresol
- 11. Subject tooth having previous or attempted pulpectomy or root canal therapy
- 12. One or two adjacent teeth in direct contact with the subject tooth requiring root canal therapy, pulpectomy or pulpotomy
- 13. Any tooth on the same side of the oral cavity as the subject tooth with a source of pain
- 14. Extraoral swelling on or around the subject tooth that has not undergone antibiotic treatment or a procedure to treat the swelling prior to RCT
- 15. Any condition that would preclude tolerance of a root canal therapy including but not limited to being in a reclined and prolonged position in a dental chair, use of a dental dam, or ability to have an open mouth for extended periods of time (>15 minutes) (e.g. history of seizure within the last 5 years, severe asthma, or extreme gag reflex)
- 16. Any other condition that the Investigator determines is unacceptable for enrollment into the study
- 17. Nonodontogenic facial pain
- 18. History of cancer within the oro-maxillofacial region
- 19. History of any cancer within the last two years, including skin cancer
- 20. History of head and/or neck radiation therapy
- 21. Immunocompromised patients (i.e. corticosteroid usage)
- 22. Any medical history that affects blood coagulation (e.g. bleeding disorders)

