## 7.11 Obturation

After the Sonendo GentleWave System treatment is completed; obturation, and coronal seal are required according to standard endodontic practices.

- 1. Dry the pulp chamber and the root canals in preparation for obturation.
- 2. Obturate the subject tooth using standard endodontic techniques. A warm vertical compaction method should be utilized as the obturation technique for this study.
- 3. A cone fit radiograph is recommended prior to completion of obturation.
- 4. Complete obturation to the full working length leaving the coronal 1-2mm for

extension of the restorative materials of each canal is recommended.

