## 7.14 Post Procedure Assessments and Evaluations

The following information will be collected post procedure;

- Diagnostic Radiographic Analysis: Periapical (PA) Parallel Radiograph, showing the periapical region surrounding the subject tooth should be collected for each visit. Additional radiographs completed as necessary by the PI will be collected for the study.
- 2. Cone Beam Computed Tomography (CBCT) radiograph post procedure is recommended.
- 3. Radiographic Evaluation of Obturation:
  - a. The PI will evaluate the radiographs to determine the level of obturation.
    - i. Short Fill: Sealer or obturation material <2mm above the apex.
    - ii. Flush Fill: Sealer or obturation material within 2mm of the apex.
    - iii. Overfill: Sealer or obturation material >2mm below the apex.
    - iv. Presence and size of sealer puff
- 4. AAE Case Difficulty Assessment: This form will be utilized by the PI after every Procedure Visit to assign a level of difficulty to a particular case.
- 5. Gracely Descriptor Differential Scale
- 6. Patient Satisfaction Survey: This is a questionnaire that asks the patient to rate their experience of the root canal procedure they had and compare it with their previous root canal procedure experience, if applicable. The questionnaire also asks the patient to indicate any sensations or pain felt during the procedure.

If the PI prescribes any antibiotics, analgesics and/or anti-inflammatory medications post procedure; these medications will be documented at subject's next study visit if the medications were taken by the subject. If the prescribed medications were not taken by the subject, the clinical site designee should make a note of this on the source document.

All subjects are instructed to contact the PI and/or clinical site designee in case of increased pain or discomfort after the procedure. If during the wait period between the Procedure Visit and next study visit, the subject has increased pain or discomfort, the PI will provide the subject with standard post-operative care and guidance.

All redacted source documentation with PI signature should be provided to the Sponsor for filing after each study visit. If changes are made to the source documents after PI signature, the updated source documents should be provided to the Sponsor for filing.

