# 7.16 Crown Placement

Subjects enrolled in the study should obtain a permanent crown per standard of care. It is recommended that crown placement should occur within six weeks of the root canal therapy procedure per standard of care. For the protocol, final crown placement date will be the date CRC obtains from the subject and/or GP and/or the Investigator.

Pain and tenderness to percussion, palpation, ill-fitting margins, open margins, high occlusal contact points with the opposing teeth or any other restoration related issues after crown placement experienced by the patient or reported by the PI and/or SD and/or Crown Placement dentist, will not be considered an adverse event but will be documented.

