#### **8.0 SCHEDULE OF VISITS**

Description	Screening	Baseline	Procedure  (+7 ds)	Post- Operative	1 day	2 days	3 days	7 days	14 days	6 mo. (± 14ds)	12 mo. (± 30ds)	18 mo. (± 30ds)	24 mo.² (± 45ds)	Unsched uled Visits
Screening Form by Screening Dentist or Pl	x													VISIUS
Images of Smile & Oclussal Surface	х													
X-Rays (Periapical) 	x	x	x	х						х	х	х	х	As needed
Medical and Dental History	х	x								х	x	х	х	As needed
Medication Regimen Review	x	x								х	х	х	х	As needed
Informed Consent		x								As needed	As needed	As needed	As needed	As needed
СВСТ		X, if applicable		X, if applicable							X, if applicable		X, if applicab le	As needed
McGill Short Form		х			x	х	х	x	х	х	x	х	х	As needed
Gracely DDS		x		x	x									
Periapical Index Score		x								х	х	х	х	As needed
General Dental and Endodontic Assessments		x								х	x	х	x	As needed
Sonendo GentleWave Treatment			x											
Root Canal Therapy			х											
Intra Assessments and Evaluations			x											
Post Operative Assessments and Evaluations				х										
Patient Satisfaction Survey				х										
AAE Case Difficulty Assessment				x										
Adverse Event Assessment			x	x						х	x	х	х	As needed

- 1. The procedure must be completed within seven days (7) of the baseline visit. For any treatment not completed within seven days of the baseline, the baseline assessments must be completed again within the time frame indicated. In addition, if a subject must return to the clinical site for completion of a procedure, as indicated in *Section 7.9 Second Procedure* Visit, this must also occur within seven days of the baseline.
- 2. Subjects may be asked to have a follow-up visit every year after the twenty-four (24) month visit for up to ten (10) years.
- 3. Only PA Parallel radiographs will be obtained.

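### PAI readers are said to be blinded to visit, but the root filling separates the Baseline film from every follow-up film, and the radiographic part of Healing is measured from Baseline

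*Combined protocol and SAP*

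**What the plan says.** Section 7.4.4 (item 6) provides up to three independent readers and says: "Independent reviewers will be blinded to the site, subject, and visit when completing the PAI score". Section 7.17.2 (item 4) repeats the statement for the follow-up films. Both give elimination of bias as the reason.

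The following places bear on whether that is achievable:

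- Section 5.2, exclusion 11, rules out: "Subject tooth having previous or attempted pulpectomy or root canal therapy".
- Section 7.11 requires the operator to: "Obturate the subject tooth using standard endodontic techniques".
- Section 7.14 treats the filling as readable on film: "The PI will evaluate the radiographs to determine the level of obturation".
- Section 7.14 also calls for a post-procedure film: "Periapical (PA) Parallel Radiograph, showing the periapical region surrounding the subject tooth should be collected for each visit". The X-ray row of the schedule in 8.0 is marked at Post-Operative.
- In the same schedule, the row "Periapical Index Score" is marked at Baseline and at 6, 12, 18 and 24 months (unscheduled visits as needed). The Post-Operative cell is empty, and 7.14 lists no PAI read.
- Section 3.1 counts a tooth as a success at 24 months if it is Healed (PAI below 3 and no clinical signs or symptoms) or Healing. Healing is a reduction from Baseline in radiolucency, in clinical signs and symptoms, or in both.
- Section 3.3 lists the independent readers' PAI as a secondary endpoint. No section says who judges radiographic reduction for the primary endpoint.

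**The concern.** Blinding to visit stops a reader's expectation from shaping a before-and-after comparison. Here the before film shows an unfilled tooth and every after film a filled one, so the reader knows which is which. A reader who expects disease before treatment may grade the Baseline film too severely. That can create a lesion that then appears to shrink, and a tooth that is not Healed at 24 months could be counted as Healing.

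The trial has a single arm, and section 13.1 sets its result against a fixed 70% from the literature. No concurrent group shares the same reading error, so it would not cancel.

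**Working it through.** **1. What a reader can see**

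| Film | Root filling on film | PA film in 8.0 | PAI in 8.0 |
|---|---|---|---|
| Baseline | No (exclusion 11) | Yes | Yes |
| Post-operative | Yes (7.11, 7.14) | Yes | No |
| 6, 12, 18, 24 months | Yes | Yes | Yes |

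The second column separates Baseline from everything later. It does not order the four follow-up films among themselves. The protocol describes no cropping or masking that would hide the filling.

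**2. Which part of the endpoint is exposed**

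Healed uses only the 24-month status. Healing through clinical signs and symptoms needs no film reader. The exposed teeth are those that are not Healed, have no clinical improvement, and would count as a success only through radiographic reduction from Baseline.

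**3. The plan's own figure (section 13.1)**

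Inputs: n = 86, null rate 0.70, alternative 0.85, two-sided binomial test at 5%.

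- Smallest count with an upper tail of at most 0.025 under 0.70: 69 of 86.
- Upper-tail error 0.0223; total two-sided size 0.0447.
- Exact power at 0.85: 0.914 (normal approximation 0.916; with continuity correction 0.891).
- Enrolment: 86 / 0.80 = 107.5, rounded up to 108.

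The stated power of about 90% and the 108 are reproduced. The sample size is not in question; only the threshold of 69 is used below.

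**4. Upper limit on the shift**

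The documents give no misgrading rate, so the inputs are assumptions: 10-20% of Baseline films over-graded, and 15-30% of teeth not Healed at 24 months.

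Shift = share over-graded × share not Healed

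- Low end: 0.10 × 0.15 = 0.015, or 1.5 points.
- High end: 0.20 × 0.30 = 0.06, or 6 points.

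The product takes over-grading to be equally common among teeth that are not Healed, and takes every such tooth to flip to success. Not all would. Some already count through clinical improvement or a true reduction, and a film graded 2 instead of 1 still shows no apical periodontitis under section 3.1. For these inputs the product is therefore an upper limit.

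**5. What such a shift would do to the test**

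Suppose the true success rate is 0.70 and a share m of the true failures is called Healing. The apparent rate is 0.70 + 0.30 × m.

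| m | Apparent rate | Chance of at least 69 of 86 |
|---|---|---|
| 0 | 0.700 | 2.2% |
| 5% | 0.715 | 4.3% |
| 10% | 0.730 | 7.9% |
| 15% | 0.745 | 13.5% |
| 20% | 0.760 | 21.6% |

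This too is an illustration over an assumed range. It shows that a few points can matter against a fixed comparator.

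**6. Would the post-operative film help?**

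It shows a filled tooth, so the filling no longer marks out the reference film. Two cues remain. Section 7.16 says: "It is recommended that crown placement should occur within six weeks of the root canal therapy procedure per standard of care". In teeth not already crowned, the post-operative film will therefore usually lack the crown seen later. Section 7.14 also records sealer puff on these films. Masking to the apical region removes the first cue but not the second.

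**The case against.** The strongest reply is that little of the blinding fails. Site, subject and follow-up time point are untouched by the filling, and the 24-month film alone decides Healed. That stands. A reader might infer that the readers are effectively unblinded, or that Baseline against follow-up is the only contrast that matters; the documents support neither.

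A second reply is that the route to the primary endpoint is not established. Section 3.1 speaks of radiolucency rather than a fall in PAI and names no judge, and 3.3 places the readers' PAI among the secondary endpoints. This stands as a gap in the protocol. If the blinded readers decide, the problem applies directly. If treating investigators decide, they know the visit and there is no blinding to rely on. Either way the protocol must say which.

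A third reply concerns the remedy. One might infer that scoring the post-operative film solves the problem, or that it should replace Baseline as the reference. The crown and sealer cues show that it would not fully solve it. Replacing the reference would contradict the Healing definition in 3.1 and the synopsis. Both points stand and shape the fix.

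Finally, section 3.3 leaves room for more reading: "Additional Radiographic Analysis may be completed". That is an open option, not a planned score.

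**Conclusion.** The claim of blinding to visit is wrong as written for Baseline against follow-up. This follows from eligibility plus required obturation, so it affects essentially every followed tooth. Blinding among the 6- to 24-month films can stand so far as the filling is concerned. The exposure is limited to teeth that would succeed only through radiographic reduction.

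The size is unknown. The 1.5 to 6 points is an upper limit under assumed inputs, against a planned difference of 15 points. It should not be read as an estimate of bias, and the documents do not show that over-grading will happen. The point rests on a protection that is stated but absent, in a single-arm comparison with nothing to cancel the error. The correction is cheap and should be made.

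**What to change.** 1. In 7.4.4 and 7.17.2, restate the blinding as covering site, subject and follow-up time point, and say that readers are not blinded to treatment status.
2. In 7.14 and 8.0, add the post-operative PA film to the PAI reading set. The same readers should score it in random order with the follow-up films, with images masked to the apical region because the permanent crown usually comes later.
3. Keep Baseline as the reference in 3.1 and the synopsis. Add a pre-specified sensitivity analysis of 24-month Healed or Healing in which radiographic reduction is measured from the post-operative score.
4. State in 3.1 that the blinded readers' scores decide whether radiolucency has been reduced.

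Cost: one more read per subject per reader. Scheduled reads rise from 5 to 6 per subject. For 108 subjects with every visit present that is 6 × 108 = 648 instead of 5 × 108 = 540 per reader, plus the image masking. No new radiograph, visit or reader is needed. Sealer may obscure the apex on some post-operative films, or help identify them, so some bias can remain.
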